5.2.4.3 Primary Analysis of Secondary Endpoint: PFS

The main analysis of PFS is based on the FAS. The number and percentage of participants experiencing a PFS event (broken down by type of event/censoring) and Kaplan-Meier plots of PFS will be presented. The median PFS and its 2-sided 80% and 95% CIs will be estimated using the Kaplan-Meier method (if participant numbers allow).

The IP status at progression of participants at the time of analysis will be summarised. This includes the number (%) of participants who were on IP at the time of progression, the number (%) of participants who discontinued IP prior to progression, the number (%) of participants who have not progressed and were on IP or discontinued IP.

A summary of the duration of follow-up for PFS is included using median (range) for censored participants (including all types of PFS censoring).

The proportion of participants alive and progression free at every 3 months (3, 6, 9, 12, etc.) and associated 2-sided 80% and 95% CIs will be estimated using the Kaplan-Meier method.

5.2.4.4 Sensitivity Analysis of PFS Endpoint

A sensitivity analysis will be performed censoring PFS at the date of the last progression-free disease assessment prior to initiation of subsequent anticancer intervention.

Separately, a sensitivity analysis will also be conducted to assess the impact of COVID-19 related deaths on PFS. That is, participants who had a PFS event due to death where the primary or secondary cause of death was COVID-19 infection or COVID-19 infection was reported as a fatal AE, will be censored on the last available tumour assessment prior to COVID-19 infection related death. This sensitivity analysis will only be performed if 5 or more participants have confirmed or suspected COVID-19 death events.

5.2.5 Secondary Endpoint: Overall Survival (OS)

OS is a secondary efficacy endpoint.

5.2.5.1 Definition

OS is defined as the time from the date of first dose until death due to any cause regardless of whether the participant withdraws from study therapy or receives another anti-cancer therapy.

5.2.5.2 Derivations

OS (months) = (date of death or censoring – date of first dose + 1) / (365.25/12).

Any participant not known to have died at the time of analysis will be censored based on the last recorded date on which the participant was known to be alive. Participants known to be alive or dead after the DCO for analysis will be censored at the DCO. Participants lost to follow-up will be censored at the date the participant is last known to have been alive. At study closure, any participant still alive after last patient last visit for the study will be censored at the date of last patient last visit.

Note: Survival calls will be made in the week following the date of DCO for the analysis, and if participants are confirmed to be alive or if the death date is after the DCO date these participants will be censored at the date of DCO. The status of ongoing, withdrawn (from the study) and “lost to follow-up” participants at the time of the final OS analysis should be obtained by the site personnel by checking the participant’s notes, hospital records, contacting the participant’s general practitioner and checking publicly-available death registries. In the event that the participant has actively withdrawn consent to the processing of their personal data, the vital status of the participant can be obtained by site personnel from publicly available resources where it is possible to do so under applicable local laws.

Note: For any OS analysis performed in the absence of survival calls being made, it may be necessary to use all relevant eCRF fields to determine the last recorded date on which the participant was known to be alive for those participants still on intervention (since the SURVIVE module is only completed for participants off IP if a survival sweep is not performed). The last date for each individual participant is defined as the latest among the following dates recorded on the eCRFs:

- AE start, stop and change in severity dates
- Admission and discharge dates of hospitalization
- Study IP date
- End of IP date
- Concomitant medication start and stop dates
- Laboratory test dates
- Date of vital signs
- Disease assessment dates on eCRF
- Start and stop dates of alternative anticancer intervention
- Date last known alive on survival status eCRF
- End of study date

Duration of follow-up for OS is reported separately for censored participants and non-censored participants as well as combined for all participants and is defined as follows:

Duration of follow-up for OS (months) = (date of death or censoring [date last known to be alive]) – date of first dose + 1) / (365.25/12).

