7.3 Lost to Follow up

A participant will be considered lost to follow-up if he or she repeatedly fails to return for scheduled visits and is unable to be contacted by the study site.

The following actions must be taken if a participant fails to return to the clinic for a required study visit:

- The site must attempt to contact the participant and reschedule the missed visit as soon as possible and counsel the participant on the importance of maintaining the assigned visit schedule and ascertain whether or not the participant wishes to and/or should continue in the study.
- Before a participant is deemed lost to follow up, the investigator or designee must make every effort to regain contact with the participant (where possible, 3 telephone calls and,

if necessary, a certified letter to the participant's last known mailing address or local equivalent methods). These contact attempts should be documented in the participant's medical record.

- Should the participant continue to be unreachable, he/she will be considered to have withdrawn from the study.

Discontinuation of specific sites or of the study as a whole are handled as part of [Appendix A](#).

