5.2.5.3 Handling of Dropouts and Missing Data

If a participant is known to have died where only a partial death date is available, then the date of death is imputed as the latest of the last date known to be alive +1 from the database and the death date using the available information provided:

- For Missing day only – using the 1st of the month of death.
- For Missing day and Month – using the 1st of January of the year of death.

If there is evidence of death but the date is entirely missing, it is treated as missing, ie, censored at the last known alive date.

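### When OS is analysed without survival calls, the SAP's last-known-alive list admits the end-of-study date, which may fall after the last real contact with a participant lost to follow-up

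*SAP*

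**What the plan says.** SAP 5.2.5.2 defines OS time as "OS (months) = (date of death or censoring – date of first dose + 1) / (365.25/12"), so each day added to a censoring date adds a day of observed survival.

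For lost participants the section states a principle: "Participants lost to follow-up will be censored at the date the participant is last known to have been alive". Protocol 10.9.4.2.2 censors on the same basis. The SAP also plans survival calls in the week after the data cut-off. For the final OS analysis it asks sites to check notes, hospital records, general practitioners and death registries for ongoing, withdrawn and lost participants.

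A second note gives a fallback: "For any OS analysis performed in the absence of survival calls being made, it may be necessary to use all relevant eCRF fields". It is introduced "for those participants still on intervention (since the SURVIVE module is only completed for participants off IP if a survival sweep is not performed"). The rule that follows is: "The last date for each individual participant is defined as the latest among the following dates recorded on the eCRFs". The list ends with "End of study date", with no exception for participants who were lost or who died.

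Protocol 7.3 describes how a lost participant leaves the study. After repeated attempts at contact (where possible three telephone calls and, if necessary, a certified letter): "Should the participant continue to be unreachable, he/she will be considered to have withdrawn from the study".

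For partial death dates, SAP 5.2.5.3 says that "the date of death is imputed as the latest of the last date known to be alive +1 from the database" and the first day of the known month, or 1 January of the known year. It sets no upper limit.

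**The concern.** Most dates on the list come from an event that needs a living participant: a dose, a laboratory sample, vital signs, a scan. An end-of-study date need not. For someone declared lost under Protocol 7.3, it may mark the day the site gave up, when nobody knew whether the participant was alive. A rule that takes the latest date then selects exactly that one.

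This would count time without contact as survival, which raises the Kaplan-Meier OS curve. It would also enter the duration of OS follow-up and the three-monthly survival proportions. In 5.2.5.3 it could date a death later than the recorded month allows. Where a death date is wholly missing, that section censors at the last-known-alive date, so time after death could be counted as survival.

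**Working it through.** The documents give no figure on this point, so there is none to reproduce. The check has three parts: what the text covers, the rules applied to example dates, and the effect on OS. All dates, lags, survival medians and loss rates are assumptions.

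**1. What the list covers**

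- The lead-in limits it to analyses without survival calls and to participants still on intervention.
- A participant who continues on intervention would normally have no end-of-study date. For that group the item does nothing, so it acts mainly on those who have left.
- The list also contains the last-alive date from the survival-status form and the dates of alternative anticancer treatment. Both fit participants off treatment, and the lead-in itself says that the survival module is for participants off treatment when there is no sweep.
- The maximum is taken for every individual participant. A programmer could therefore apply it to everyone.
- An analysis without calls is foreseeable. SAP 4.2.1 allows additional data cuts, SAP section 3 notes that the survival sweep is not in the protocol, and 5.2.5.2 itself provides for the case.

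**2. The rules applied to dates**

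*Lost participant.* First dose 3 Oct 2022, last real contact 1 Feb 2023, which is 121 days later. One month is 365.25/12 = 30.4375 days. Censored at last contact, OS time is (121 + 1)/30.4375 = 4.01 months. With an end-of-study date *k* days after that contact, it is (122 + *k*)/30.4375:

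| *k* (days) | OS time (months) | Added |
|---|---|---|
| 14 | 4.47 | 0.46 |
| 30 | 4.99 | 0.99 |
| 60 | 5.98 | 1.97 |
| 91 | 7.00 | 2.99 |
| 120 | 7.95 | 3.94 |

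*Partial death date.* Same first dose, last contact 20 Feb 2023, death in March 2023 with the day unknown. Imputed date = max(last alive + 1, 1 Mar 2023):

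| End-of-study date | Imputed death | OS (months) | In known month? |
|---|---|---|---|
| not used | 1 Mar | 4.93 | yes |
| 20 Mar | 21 Mar | 5.59 | yes |
| 31 Mar | 1 Apr | 5.95 | no |
| 20 Apr | 21 Apr | 6.60 | no |
| 31 May | 1 Jun | 7.95 | no |

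The imputed date leaves the known month only if the end-of-study date is on or after the last day of that month.

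**3. Effect on OS if every lost participant is affected**

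*Median.* Large-sample Kaplan-Meier simulation with exponential survival, true median 6 or 12 months, follow-up to 18 months, lags of 1 and 3 months:

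| Share lost | Rise in median OS (months) |
|---|---|
| 5% | 0.03 to 0.11 |
| 10% | 0.08 to 0.22 |
| 20% | 0.17 to 0.53 |

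*Survival proportions.* 4,000 simulated cohorts of 21, follow-up 6 to 18 months, 2 or 4 lost between months 1 and 9, lag 3 or 6 months but not beyond the cut-off. Estimated 12-month OS rises by 1.0 to about 4.5 percentage points (true median 6 months) or 0.9 to 3.7 points (true median 12 months). Estimated 6-month OS rises by about 0.5 to 2 points. Censoring at the true last contact gave no bias.

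*For scale.* With 21 participants and a true proportion of 25% to 50%, a simple binomial 80% interval has a half-width of 1.28 × √(p(1 − p)/21), about 12 to 14 points. The 95% half-width is about 19 to 21 points.

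**The case against.** A reader might infer that the SAP censors lost participants after contact failed as a matter of course, and that OS is therefore biased upward. The documents do not support that, for four reasons.

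- **Scope.** The list is a fallback that may be needed, only without survival calls, and it is introduced for participants on treatment. An explicit sentence covers lost participants, and a specific sentence should prevail over a fallback note. The calls and record checks are further safeguards.
- **Unknown source.** Neither document says how the end-of-study date is completed for someone lost or dead. It could be the last contact. For a participant who withdraws at a visit or call, it is sound evidence of life.
- **Deaths.** A reader might also infer that imputed deaths will fall after the known month. But 5.2.5.3 does not name the 5.2.5.2 list, and a date after a known death is hardly one on which the participant was known to be alive.
- **Size.** Someone lost while on weekly dosing has frequent recorded contacts. Lags of three months fit the three-monthly survival follow-up in Protocol 8.2.3 better, and the six-month lag has no source. Even the largest shifts are small beside the intervals for 21 participants.

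These arguments make the point conditional; they do not remove it. The sentence on lost participants states a principle but no algorithm, and the list is the only field-by-field derivation of last known alive in the SAP. Its wording is wider than its lead-in. Survival calls help a lost participant only if that person or their records can be traced. The missing upper limit in 5.2.5.3 stands whatever feeds it.

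**Conclusion.** The concern holds in conditional form. In an OS analysis without survival calls, the rule as worded can censor a lost participant after the last real contact, against the SAP's own statement of principle. This requires that the list be applied beyond participants on treatment and that the end-of-study date be administrative. The documents settle neither.

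An imputed death can fall after the known month or year only if the same date also feeds 5.2.5.3 and falls on or after the last day of that period.

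The direction is favourable to the drug and the size is modest: about 0.03 to 0.53 months on the median for 5% to 20% lost with lags of 1 to 3 months, and about 1 to 4.5 points on 12-month OS in the cohort simulation. These figures assume that every lost participant is affected, and the upper ends need heavy loss and long lags. They illustrate the mechanism and do not predict the bias in this trial. OS is secondary and descriptive, no hypothesis is tested, and the response rate is untouched. The change is still worth making, because a stated maximum rule can return a wrong date and the correction is cheap.

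**What to change.** - In SAP 5.2.5.2, delete the end-of-study date from the list, or admit it only when the recorded reason shows direct contact with the living participant, such as a withdrawal the participant made in person or by telephone.
- State that 5.2.5.3 uses the same contact-based date.
- In 5.2.5.3, do not allow an imputed death date after the last day of the known month (or of the known year, if the month is missing), and query the site when the last-alive date conflicts with the recorded death.

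The cost is a few words of SAP text and minor programming, with no new data collection. Little information is lost, because a genuine final visit should already be captured by other listed dates. OS may look slightly less favourable if participants are lost.

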5.2.5.3 Handling of Dropouts and Missing Data

If a participant is known to have died where only a partial death date is available, then the date of death is imputed as the latest of the last date known to be alive +1 from the database and the death date using the available information provided:

- For Missing day only – using the 1st of the month of death.
- For Missing day and Month – using the 1st of January of the year of death.

If there is evidence of death but the date is entirely missing, it is treated as missing, ie, censored at the last known alive date.

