10.9.4.2.2 Secondary Efficacy Endpoint(s)

The secondary efficacy endpoints are CR rate, DoR, PFS and OS.

Duration of Response

Duration of response is defined as the time from the first objective response of CR or PR to the time of documented disease progression or death (in the absence of disease progression). It will be summarised using descriptive statistics and KM plots where there are sufficient numbers of responders.

Progression Free Survival

PFS is defined as the time from first dose date to documented disease progression, or death (by any cause in the absence of progression), regardless of whether the participant withdraws from study treatment or receives another anti-cancer therapy prior to progression. Participants who have not progressed or died at the time of analysis will be censored at the time of the latest date of assessment from their last evaluable assessment.

The PFS time will always be derived, based on scan/assessment dates, not visit dates.

Assessments/scans contributing towards a particular visit may be performed on different dates. The following rules will be applied:

- Date of progression will be determined, based on the earliest of the dates of the component that triggered the progression.
- When censoring a participant for PFS, the participant will be censored at the latest of the dates contributing to a particular overall visit assessment.

KM plots and estimates will be provided.

Overall Survival

Overall survival is defined as the time from first dose until the date of death from any cause. Any participant not known to have died by the analysis DCO date will be censored based on the last recorded date on which the participant was known to be alive. KM plots and estimates will be provided.

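### SAP 5.2.5.3 censors a participant known to have died when the death date is wholly missing, against the SAP's and protocol's own rule on who is censored for OS

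*SAP*

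**What the plan says.** SAP 5.2.5.1 defines the endpoint: "OS is defined as the time from the date of first dose until death due to any cause". SAP 5.2.5.2 then says who is censored at last contact: "Any participant not known to have died at the time of analysis will be censored based on the last recorded date". Protocol 10.9.4.2.2 agrees: "Any participant not known to have died by the analysis DCO date will be censored". Participants whose death falls after the DCO are censored at the DCO.

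SAP 5.2.5.3 deals with incomplete death dates in two ways.

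- **Partial date.** Two candidate dates are compared: "the date of death is imputed as the latest of the last date known to be alive +1 from the database"; the other candidate is built from whatever part is known. If only the year is known: "For Missing day and Month – using the 1st of January of the year of death". The death stays an event.
- **No date.** "If there is evidence of death but the date is entirely missing, it is treated as missing". The SAP spells this out as last-known-alive censoring, so the death does not count as an event.

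SAP section 3, which lists changes from the protocol's planned analysis, does not mention this rule. The only OS sensitivity analysis (SAP 5.2.5.5) concerns COVID-19 deaths.

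**The concern.** The event in OS is death. A rule that censors a participant because death is known but undated makes censoring depend on the outcome, which is what Kaplan-Meier assumes does not happen. The event is lost although the fact of death is not in doubt.

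The situation is foreseeable. SAP 5.2.5.2 sends sites to notes, hospital records, general practitioners and death registries for withdrawn and lost participants. Where consent to data processing has been withdrawn, it seeks vital status from public sources. Such sources could confirm a death without dating it, although the documents do not say how often.

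At stake are the OS curve, its median and its 3-monthly estimates in cohorts of about 21. SAP 5.2.5.4 also tabulates both OS events and participants who have died, so the two counts could disagree even for deaths before the DCO.

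**Working it through.** The documents give no OS sample size, event count or expected number of undated deaths, so there is no planned figure to reproduce.

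**1. Who is censored**

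| Source | Participant known to have died on or before the DCO |
|---|---|
| SAP 5.2.5.2 | not within the group to be censored |
| Protocol 10.9.4.2.2 | not within the group to be censored |
| SAP 5.2.5.3, partial date | event |
| SAP 5.2.5.3, no date | censored at last known alive |

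The last row stands alone.

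**2. The date rule on an example.** Let the last date known alive be 20 May 2023, so the floor (last known alive + 1 day) is 21 May 2023.

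- Month known (May 2023): later of 21 May and 1 May = 21 May. Event.
- Year known (2023): later of 21 May and 1 January = 21 May. Event.
- Nothing known: the floor is still 21 May, but the participant is censored at 20 May.

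In the first two cases the partial date sets nothing and the floor alone gives the death date. Losing the year as well changes the event status, not the date available.

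**3. The Kaplan-Meier step removed.** Let r be the number at risk at last known alive + 1 day, including this participant. After that day the participant has left the risk set under either rule. From then on:

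curve with the event counted = curve under the SAP rule × (1 − 1/r).

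The factor is 0.952 for r = 21, 0.933 for 15, 0.900 for 10 and 0.800 for 5. For example, at r = 8 an estimate of 50% would be 50% × 7/8 = 43.8%. These values of r are illustrations.

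**4. Average effect, by simulation.** All settings are assumptions: 21 participants, exponential survival with median 6 or 12 months, uniform administrative censoring at 6 to 18 months, 1 to 3 undated deaths chosen at random, last contact 0 to 3 months before death (in line with the roughly 3-monthly contacts in protocol 8.2.3), 4,000 trials per scenario. The 21 is the planned response-evaluable number per cohort; OS uses the full analysis set.

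| True median | Undated deaths | OS at | All dates known | SAP rule | Event at last known alive + 1 |
|---|---|---|---|---|---|
| 12 months | 1 | 12 months | 49.9% | 53.2% | 49.9% |
| 12 months | 2 | 12 months | 50.2% | 56.9% | 50.0% |
| 12 months | 3 | 12 months | 49.7% | 60.1% | 49.5% |
| 6 months | 1 | 6 months | 49.8% | 51.7% | 49.3% |
| 6 months | 2 | 6 months | 50.0% | 54.0% | 49.1% |
| 6 months | 3 | 6 months | 50.0% | 56.2% | 48.7% |

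One undated death raises the estimate by 51.7 − 49.8 = 1.9 to 53.2 − 49.9 = 3.3 points; three raise it by 6.2 to 10.4 points. With one undated death the typical median moves from 12.1 to 13.4 months, or from 6.0 to 6.35.

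**5. Is the shift always upward?** Take four deaths, at months 6, 10, 20 and 24. The month-20 death is undated, with last contact at month 2. OS at 12 months:

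- All dates known: 3/4 × 2/3 = 50%.
- SAP rule (censored at month 2): 2/3 × 1/2 = 33.3%.
- Event at last known alive + 1: 3/4 × 2/3 × 1/2 = 25%.

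Here the SAP rule is too low, and counting an early event is lower still. A long gap before death shrinks the risk set for other people's deaths.

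**The case against.** Five points can fairly be made for the plan.

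- **The imputation rule is written for partial dates only, and the floor is there to prevent impossible dates.** True, so applying it to a wholly missing date extends the rule. But the floor needs no part of the death date and already decides the date alone in some partial cases. The sentence's term for the trigger, evidence of death, might also mean weaker certainty than knowledge of death; the SAP does not say so, and the fix can require that death be established.
- **A wholly undated death often cannot be placed before the DCO**, because survival calls are made in the week after it and later deaths are censored at the DCO. This stands. A known month or year helps settle the matter, and a fix that ignores the question would be incomplete.
- **A reader might infer that the rule can only bias OS upward.** Relative to counting the event, it can only raise the curve. Relative to the truth, the upward bias is an average: step 5 is a counterexample, and in simulations with one undated death, true median 6 months and a gap of 6 to 18 months, the SAP estimate at 6 months fell below the all-dates-known estimate in around 3 in 10 trials.
- **The imputed date can be clearly too early for lost participants.** With three undated deaths, median 6 months and gaps of 6 to 18 months, counting events at last known alive + 1 is about 4 points low at 6 months, and its mean absolute error (about 4.4 points) is essentially that of the SAP rule.
- **The death is not hidden.** SAP 5.2.5.4 counts participants who died, and SAP 5.6.3 and protocol 9.4.3 summarise or list deaths. This limits the harm but does not correct the OS estimate.

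A reader might also infer that the death is lost from PFS. The documents do not support that: SAP 5.2.5.3 governs OS, and SAP 5.2.4.2 has separate PFS rules that say nothing of an undated death.

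**Conclusion.** The inconsistency is established from the text alone: one sentence of SAP 5.2.5.3 censors known deaths, against SAP 5.2.5.2, protocol 10.9.4.2.2 and the partial-date rule beside it, and it is not declared as a change from the protocol.

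The size is conditional. The figure of about 2 to 3 points for one undated death rests on 21 participants, exponential survival and a last contact no more than 3 months before death. The direction is upward on average, not in every dataset. No PFS effect is shown.

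Materiality is low. OS is a secondary, descriptive endpoint with no hypothesis test, and the 3-monthly contacts and record checks should make wholly undated deaths rare. The sentence should still be corrected, because a known event is dropped by rule and the repair is small.

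**What to change.** Replace the final sentence of SAP 5.2.5.3 with:

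> If death is established to have occurred on or before the DCO but the date is entirely missing, the participant is counted as an OS event with death imputed at last date known alive + 1; if it cannot be established that death occurred on or before the DCO, the participant is censored at the last known alive date. Such cases are flagged and listed, and a sensitivity analysis censors all of them at the last known alive date.

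The cost is this replacement text, a flag and listing, and one extra OS run that is needed only if such a case occurs. It is best settled before database lock. The downside is that the imputed date is the earliest possible, so OS becomes conservative, noticeably so when the gap since last contact is long. The listing (with last-contact dates) and the sensitivity analysis let a reader judge that.
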